**Table 3**      **Outcome and Event Dates for PFS Analysis**

Scenario	Date of Event / Censoring	Outcome
No baseline assessment	Date of first study treatment	Censored a
Progression or death $\leq$ xx weeks after last tumor assessment or $\leq$ xx weeks after treatment start date, where xx is 16 weeks if the last assessment is at Screening or Cycle 3 (Evaluation Visit 1), 20 weeks if the last assessment is at Cycle 5 (Evaluation Visit 2), and 24 weeks if the last assessment is at Cycle 7 (Evaluation Visit 3) or later.	Date of progression or death	Event
Progression or death $>$ xx weeks after the last tumor assessment, where xx is 16 weeks if the last assessment is at Screening or Cycle 3 (Evaluation Visit 1), 20 weeks if the last assessment is at Cycle 5 (Evaluation Visit 2), and 24 weeks if the last assessment is at Cycle 7 (Evaluation Visit 3) or later.	Date of last adequate tumor assessment	Censored
No progression	Date of last adequate tumor assessment	Censored
Treatment discontinuation due to "Disease progression" without documented progression	Not applicable	Information collected on treatment discontinuation page is ignored since outcome should be derived based on documented progression only. General censoring rule is applied.
New anti-cancer therapy given	Date of last adequate tumor assessment before anti-cancer therapy is given	Censored

aIf the subject dies  $\leq$  16 weeks after treatment start date, the death is an event with date on death date.

Kaplan-Meier estimates (product-limit estimates) will be presented together with a summary of associated statistics (median survival time; 6- and 12-month survival rate estimates) including the corresponding two-sided 95% confidence intervals (CIs). The CI for the median will be calculated according to Brookmeyer and Crowley (1982), and CIs for the survival function estimates at the aforementioned time points will be derived using the log-log transformation according to Kalbfleisch and Prentice (1980) (conftype=loglog default option in SAS PROC LIFETEST). The estimate of the standard error will be computed using Greenwood's formula.

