## 7.2.5

### Computed Tomography or Magnetic Resonance Imaging Scans for Tumor Assessment at Baseline

Baseline imaging will be performed up to 21 + 7 days prior to the first M4112 administration in order to establish baseline disease status of target and nontarget lesions according to RECIST 1.1 ([Appendix III](#)). A chest X-ray should be performed before a CT or MRI scan to exclude prohibitive entry criteria.

In addition to a baseline assessment prior to start of treatment, during treatment, CT scans (with contrast media, unless contraindicated) will be done for tumor assessments within 7 days prior to Day 1 of Cycles 3, 5, and 7 and thereafter every 3 cycles until progressive disease. These assessments can also be done by MRI (if MRI is used, CT of chest is mandatory), using the same method at all subsequent assessment time points. Imaging should be performed of the chest/abdomen/pelvis (plus other regions as specifically required for specific tumor types), and other established assessments of tumor burden if CT/MRI imaging is insufficient for the individual subject. A brain CT/MRI scan should be performed, if clinically indicated by development of new specific symptoms. Skin metastasis can be used as target lesions according to RECIST 1.1 ([Appendix III](#)) using measurements by caliper, if they fulfill RECIST 1.1 for target lesions. All the scans performed at baseline need to be repeated at subsequent visits for tumor assessment. In general, lesions detected at Baseline need to be followed using the same imaging methodology and preferably the same imaging equipment at subsequent tumor evaluation visits.

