### 14.1 Progression Free Survival

Progression free survival (PFS) time, according to RECIST 1.1 as assessed by the Investigator, is defined as the time from first study treatment to the date of the first documentation of objective PD or death due to any cause, whichever occurs first.

PFS data will be censored on the date of the last adequate tumor assessment for patients who do not have an event (PD or death) or for patients with an event after two or more subsequent missing response assessments (i.e., twice the scheduled time interval between two subsequent response assessments – this interval is 8 weeks through Cycle 7, and 12 weeks thereafter). Patients who do not have a baseline tumor assessment or who do not have any postbaseline tumor assessments will be censored at treatment start date unless death occurred on or before the time of the second planned tumor assessment, in which case the death will be considered an event.

Data will be taken from the “Assessment of Disease Based on Imaging” CRF page. The date of the overall response assessment is the earliest date for imaging of target, nontarget, and new lesions taken at that response assessment.

The censoring and event date options to be considered for the PFS analysis are presented in **Table 3**. The last adequate tumor assessment is defined as a tumor assessment with a result other than “NE” or “NA”.

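### When the last scan before a PFS event is Screening, SAP Table 3 can code an event shortly before week 16 as event or as censored, and can date censoring before first dose

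*SAP*

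**What the plan says.** SAP section 14.1 defines PFS as the "time from first study treatment to the date of the first documentation of objective PD or death due to any cause". The time origin is therefore first dose.

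Table 3 then assigns outcomes.

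- **Event row.** Progression or death counts if it falls within xx weeks of the last assessment or within xx "weeks after treatment start date, where xx is 16 weeks if the last assessment is at Screening or Cycle 3 (Evaluation Visit 1".
- **Censored row.** Progression or death more than xx "weeks after the last tumor assessment, where xx is 16 weeks if the last assessment is at Screening or Cycle 3" is censored. This row names Screening but has no treatment-start condition. Its date column reads "Date of last adequate tumor assessment".
- **Rows for no progression and for new anti-cancer therapy.** Both also censor at the last adequate assessment, the latter at the last one before the therapy.

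The section text adds three things. Subjects without a baseline scan or without any post-baseline scan "will be censored at treatment start date unless death occurred on or before the time of the second planned tumor assessment"; such a death is an event. An event after at least two missed assessments is censored, and a parenthesis equates this with two scheduled intervals (8 weeks each through Cycle 7, then 12). On adequacy: "The last adequate tumor assessment is defined as a tumor assessment with a result other than" NE or NA.

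Protocol section 7.2.5 sets the scan timing: "Baseline imaging will be performed up to 21 + 7 days prior to the first M4112 administration".

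**The concern.** The two rows are meant to divide late events from timely ones. They do so only if both count from the same date. For a Screening scan they do not: the event row can count from first dose and the censored row counts from the scan, which may be up to four weeks earlier. An event in that gap satisfies both rows, and the table gives no order of precedence. Two programmers could follow it and reach different outcomes for the same subject.

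The censored row also points to a scan taken before the PFS clock starts. What is at stake is whether an early progression is counted as an event, plus PFS times that cannot be real.

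**Working it through.** **Inputs.** Scans fall within 7 days before Day 1 of Cycles 3, 5 and 7, then every three 28-day cycles (Protocol 7.2.5). The Screening scan is s days before first dose, s from 0 to 28 (Protocol 7.2.5). Duration is stop minus start plus 1 day (SAP section 9). Let e be days from first dose to the event; 16 weeks is 112 days.

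**1. The plan's own cut-offs.** Scan weeks from first dose are 8, 16, 24, 36 and 48, with 0 for treatment start. Two intervals give:

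- start to Cycle 5: 16 − 0 = 16
- Cycle 3 to Cycle 7: 24 − 8 = 16
- Cycle 5 to Cycle 10: 36 − 16 = 20
- Cycle 7 to Cycle 13: 48 − 24 = 24

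These match Table 3. The 16 weeks for Screening is reproduced only when counted from treatment start. Counted from a scan 28 days before dosing, Cycle 5 is 16 + 4 = 20 weeks away.

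**2. Overlap.** Event row: e + s ≤ 112 or e ≤ 112, which reduces to e ≤ 112. Censored row: e + s > 112. Both hold when 112 − s < e ≤ 112, a window s days wide. The censored row's PFS is −s + 1.

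| s (days) | Days after first dose in both rows | Width (days) | PFS if censored (days) | On-schedule Cycle 5 scan days (105–112) in both rows |
|---|---|---|---|---|
| 1 | 112 | 1 | 0 | 1 of 8 |
| 7 | 106–112 | 7 | −6 | 7 of 8 |
| 14 | 99–112 | 14 | −13 | 8 of 8 |
| 21 | 92–112 | 21 | −20 | 8 of 8 |
| 28 | 85–112 | 28 | −27 | 8 of 8 |

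If the last assessment is post-baseline, the treatment-start clause in the event row adds nothing and the overlap is 0.

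**3. Example.** Screening scan 21 days before dosing, Cycle 3 scan missed, PD on the Cycle 5 scan at e = 108. From the scan this is 129/7 = 18.4 weeks; from start it is 108/7 = 15.4 weeks. Table 3 gives an event at 109 days and also a censoring at −20 days.

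**4. What the text makes of the example.** One assessment was missed, fewer than two, so the count says event. The parenthesis turns two missed assessments into 2 × 8 = 16 weeks. From the Screening scan, 18.4 > 16 says censored; from first dose, 15.4 ≤ 16 says event. The text does not say which date to count from.

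**5. Pre-dose date beyond the overlap.** PD first seen at Cycle 7 (days 161–168) after missed Cycle 3 and Cycle 5 scans is in the censored row only. For s = 21 and e = 161 it is 182/7 = 26 weeks after the scan, and its date is still Screening: −20 days. The text's treatment-start rule does not literally reach this subject, because the PD scan is itself post-baseline.

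**The case against.** The best defence is that the rest of the plan shows the intent. The treatment-start clause in the event row has an effect only when the last scan is Screening, so it was evidently put there to make these subjects events; the censored row just failed to repeat it. Protocol section 7.3 counts missed assessments without the two-interval parenthesis, which favours event for PD at Cycle 5 after one missed scan. Deaths with no post-baseline scan are settled by the text of both documents: event up to the second planned assessment, otherwise censored at treatment start. A baseline scan might also be held not to have an adequate result.

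Much of this stands. A reader might infer that every subject whose last scan is Screening sits in both rows. The documents do not support that: the event must fall in the s-day window, and the subject must have no Cycle 3 scan. Nor is it right that such deaths are left open; there the table merely contradicts its text.

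What does not stand is that the text cleanly resolves progression. The parenthesis in SAP 14.1 gives the censored row a literal basis. Holding the baseline scan inadequate does not help either, because the censored row would then give no date.

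**Conclusion.** Table 3 is wrong as written for a narrow set of subjects. With Screening as the last scan before the event, an event in a window of s days (at most 28) ending 16 weeks after first dose is assigned both outcomes. For deaths the text supplies the answer; for PD it is ambiguous.

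The pre-dose date is a separate defect. It can arise in the censored row, the no-progression row and the new-therapy row whenever no adequate post-baseline scan comes first. For subjects with no post-baseline scan at all, it contradicts the text's treatment-start rule.

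A reader might infer that negative PFS times bias the Kaplan-Meier curve. They do not by themselves: a subject censored at day −27, 0 or 1 is in no later risk set, so the estimates match those under censoring at treatment start. What matters is status. Recoding an event as censored removes it and raises the curve. In a usual cohort of 3 with all still at risk, one event takes the estimate from 1 to 2/3; censored, it leaves no step.

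The impact is limited. PFS is a descriptive secondary endpoint, and the documents give no basis for how many subjects would be affected. The result assumes the Screening scan can count as adequate and takes Cycle 5 scans on days 105–112, ignoring visit windows.

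**What to change.** Make two edits to Table 3.

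1. In the censored row, require more than xx weeks after the last tumor assessment **and** more than xx weeks after treatment start. Post-baseline cases are unchanged.
2. Add a row: *no adequate post-baseline assessment before the event or censoring point, and no event within 16 weeks of treatment start: censored at date of first study treatment*. State that this row takes precedence over the other censoring rows, and that an event after new anti-cancer therapy does not count as an event here.

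The second edit also covers PD first seen at Cycle 7 after missed Cycle 3 and Cycle 5 scans. Afterwards the overlap is 0 days for every s, and the shortest censored time is start − start + 1 = 1 day. The cost is a short revision of one table; no new data are needed.

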### 7.3 Efficacy Assessments

The tumor response assessments will be performed at time points indicated in the Schedule of Assessments (Table 1, Table 2, and Table 3) and as discussed in Section 7.2.5.

- **Clinical endpoints:** Time to tumor response, objective response, best overall response (BOR), DCR, duration of response (DOR), and progression-free survival per Investigator according to RECIST 1.1 (Appendix III). A CT or MRI scan is mandatory for confirming any CR and partial response (PR) after at least 4 weeks following first assessment.
- **Progression Free Survival (PFS)** time is defined as the time from start date to the date of the first documentation of objective progression of disease or death due to any cause, whichever occurs first. PFS data will be censored on the date of the last adequate tumor assessment for subjects who do not have an event (progressive disease or death), for subjects who start a new anticancer therapy prior to an event or for subjects with an event after 2 or more missing tumor assessments. Subjects who do not have a baseline tumor assessment or who do not have any post-baseline tumor assessments will be censored on the treatment start date unless death occurred on or before the time of the second planned tumor assessment in which case the death will be considered an event.
- **Best Overall Response (BOR)** will be determined according to RECIST 1.1 (Appendix III). It is defined as the best response obtained among all tumor assessment visits after the date of first study drug administration until documented disease progression. The BOR rate is defined as the number of subjects with BOR was either confirmed CR or PR, relative to the number of subjects belonging to the study of interest.
- Only tumor assessments performed before the start of any further anticancer treatment will be considered in the assessment of BOR. Clinical deterioration will not be considered as documented disease progression.
- **Disease Control Rate (DCR)** is defined as a BOR of complete response (CR), PR or stable disease. Both CR and PR must be confirmed by repeat assessments performed no less than 4 weeks after the criteria for response are first met. DCR is the proportion of subjects with disease control.

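### SAP Table 3 censors PFS at new anticancer therapy without the protocol's timing condition, so two of its rows conflict and no row order reproduces the protocol rule

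*SAP*

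**What the plan says.** Protocol Section 7.3 defines PFS as time to first documented progression or death. Its grounds for censoring at the last adequate tumor assessment include new therapy, but only "for subjects who start a new anticancer therapy prior to an event".

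SAP Section 14.1 keeps the endpoint, running to "the date of the first documentation of objective PD or death due to any cause, whichever occurs first". Its text censors "for patients who do not have an event (PD or death) or for patients with an event after two or more subsequent missing response assessments" and does not mention new therapy. It then refers to Table 3 for the censoring and event dates. Two rows of that table matter here:

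- Progression or death within the stated gap (16, 20 or 24 weeks, depending on the last assessment): dated at "Date of progression or death", outcome Event.
- "New anti-cancer therapy given": dated at "Date of last adequate tumor assessment before anti-cancer therapy is given", outcome Censored.

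The second row has no condition on timing relative to progression or death, and the table does not say which row prevails when both apply. The visible text of SAP Section 7, which lists changes from the protocol, does not mention PFS censoring.

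**The concern.** Table 3 is the only place in the SAP that states the new-therapy rule for PFS, and it omits the condition that makes the protocol rule work. Moving to another drug after progression is a natural sequence: Protocol Section 5.5.1 withdraws subjects at progression, with exceptions.

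Consider progression at the Week 8 scan and a new drug at Week 10. "The last adequate tumor assessment is defined as a tumor assessment with a result other than" NE or NA, so the progression scan is itself adequate. If it is also the last scan before the new drug, the last row keeps the date and changes only the status, from event to censored. Doing this routinely would remove real progressions from the Kaplan-Meier estimate and push median PFS and the 6- and 12-month rates upward. The opposite choice by the programmer creates the opposite departure from the protocol.

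**Working it through.** The plan gives no expected PFS, event count or power for this endpoint, so there is no figure to reproduce. The check is a comparison of the rules, followed by an illustration of size.

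**Step 1. Two subjects under each rule.** Subject A has progression at a timely scan and then starts new therapy. Subject B starts new therapy without progression and then progresses or dies within the gap limit (for example stable at Week 8, new drug at Week 10, death at Week 14).

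| Source | Subject A | Subject B |
|---|---|---|
| Protocol 7.3 | Event | Censored |
| SAP 14.1 definition and text | Event | Event (new therapy not mentioned) |
| SAP Table 3, timely progression or death row | Event | Event |
| SAP Table 3, last row | Censored | Censored |
| Table 3, Event row applied first | Event (agrees with protocol) | Event (disagrees) |
| Table 3, last row applied first | Censored (disagrees) | Censored (agrees) |

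No fixed order of the two rows gives the protocol outcome for both subjects. Only the missing condition separates them. SAP Section 14.2 has the equivalent for best overall response: for disease control it uses only assessments before documented progression or further anticancer treatment.

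**Step 2. Size if the last row were applied first.** Inputs from the documents:

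- Scans at about Weeks 8, 16 and 24, then every 12 weeks (Protocol 7.2.5).
- One month is 30.4375 days (SAP Section 9), so 6 months is 6 × 30.4375 / 7 = 26.1 weeks. The 6-month rate therefore reflects the first three scans.

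Assumptions not in the documents:

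- Exponential latent progression with median m months.
- No deaths or dropout.
- A fraction f of progressors has a recorded later therapy and is censored at the progression scan.

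Formulas: λ = ln 2 / (m × 30.4375 / 7); h = 1 − exp(−8λ) per 8-week interval; 6-month PFS = [1 − h(1 − f)]³.

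For m = 3, the median is 13.04 weeks, λ = 0.0531 and h = 0.346.

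- f = 0 (protocol rule): (1 − 0.346)³ = 0.28.
- f = 0.50: (1 − 0.346 × 0.50)³ = 0.827³ = 0.57.

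| 6-month PFS | f = 0 | f = 0.25 | f = 0.50 | f = 0.75 |
|---|---|---|---|---|
| m = 2 | 15% | 27% | 45% | 69% |
| m = 3 | 28% | 41% | 57% | 76% |
| m = 4 | 38% | 50% | 64% | 81% |

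For m = 3 the Kaplan-Meier median is 16, 24, 36 and 72 weeks across the same values of f. Deaths without progression cannot be followed by new therapy, so including them would dilute the shift.

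The error from applying the Event row first was not quantified. It depends on how many subjects start new therapy before progression and then have a recorded event.

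**The case against.** A reader might infer that the SAP does censor every progressor who moves to another drug, and that reported PFS would be inflated by the amounts above. The documents do not support that. The PFS definition, the censoring text in 14.1, the Event row and Protocol 7.3 all make progression followed by therapy an event; only the last row read alone says otherwise. The row labels are shorthand and need to be read together. The no-progression row, read alone, would censor a timely death that the Event row counts. This part of the objection stands.

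It does not settle the matter, because the same reading makes Subject B an event too, contrary to the protocol. For B, the last row must override the Event row; for A, it must not.

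The objection to size also stands. The values of f have no source in the documents. Recorded later therapy may be limited: Part IA has one Safety Follow-up Visit at 30 ± 3 days, SAP Section 12 defines concomitant treatment only to 30 days after the last dose, and treatment may continue past RECIST progression (Protocol 5.5.1). Subject B may be uncommon, since subjects without progression at End of Treatment are not followed for it (Protocol 7.3).

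The stakes are modest: about 24 subjects were planned for Part IA, and the SAP provides one abbreviated final analysis. The planned listings and swimlane plot would show a progression that had been censored, though they would not correct the Kaplan-Meier estimate.

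**Conclusion.** The point holds as a conflict within Table 3 and between Table 3 and the protocol. The protocol's timing condition was dropped, the visible list of changes does not declare this, and no order of the rows restores it. A progressor with later therapy can be censored in error; it is not established that such subjects would be.

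If the last row prevailed, PFS would be biased upward by an amount that depends on the unknown fraction of progressors with recorded later therapy. Under the assumptions shown, 6-month PFS for a 3-month median would rise from 28% to between 41% and 76% for f from 0.25 to 0.75. These figures are a worst case under one reading, not an estimate for this trial. PFS is secondary (SAP 5.1) and all analyses are descriptive (SAP Section 9), so no error rate or sample size is affected. The correction should be made, but it does not threaten the primary objective.

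**What to change.** In SAP Table 3, change the scenario in the last row to *New anti-cancer therapy started before documented progression or death*. State that progression documented on or before the start of new therapy is an event on the progression date, subject to the missed-assessment rule. Add the protocol's timing condition to the censoring text of 14.1, so that text, table and Protocol 7.3 agree.

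The cost is a short wording change and one condition in the PFS program, with no new data. SAP Section 6 requires approval of the plan before database lock, so the correction belongs in the plan itself.

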## 14.2      Best Overall Response & Disease Control Rate

Best Overall Response (BOR) will be determined according to RECIST 1.1. It is defined as the best response obtained among all tumor assessment visits after the date of first study drug administration until documented disease progression. The BOR rate is defined as the number of subjects with BOR either confirmed CR or PR, relative to the number of subjects belonging to the study of interest.

Only tumor assessments performed before the start of any further anticancer treatment will be considered in the assessment of BOR. Clinical deterioration will not be considered as documented disease progression. BOR will be based on the investigator assessment of overall response and is defined as the best result obtained among all tumor assessment visits from baseline until end of treatment or determination of progressive disease. Local evaluations of target, non-target and new lesions are used to assess BOR. The date of the overall response assessment is the earliest date for imaging of target, non-target and new lesions of images taken at that response assessment.

BOR will be defined as the best response across all time points (for example, a subject who has SD at the first assessment, PR at the second assessment, and PD at the last assessment has a BOR of PR). The order to obtain the BOR is the following: CR, PR, SD, PD and NE.

BOR will be summarized by tabulating the number and percentage of subjects with CR, PR, SD, PD or NE as BOR. The table will also include the objective response rate (ORR) and the corresponding 95% Clopper-Pearson confidence intervals (Clopper & Pearson, 1934). The ORR will be defined as the rate of subjects who achieve either a CR or PR.

Disease control rate (DCR) is based on each subject's confirmed BOR according to RECIST 1.1 as assessed by the Investigator. Tumor assessments after the treatment start date, and prior to documented disease progression or start of further anticancer treatment are taken into consideration in deriving the BOR. Clinical deterioration is not considered as documented disease progression. If a tumor assessment was performed on the same day as the start of a new anti-cancer therapy, it is assumed that the tumor assessment was performed prior to the start of the new anti-cancer therapy; therefore, this tumor assessment is included in the assessment of BOR.

**Table 4** summarizes the derivation rules described by Eisenhauer, et al. for the BOR when confirmation from subsequent assessment is needed.

**Table 4** Best Overall Response When Confirmation of Response is Required

Overall Response 1st Time Point	Overall Response Subsequent Time Point	Best Overall Response
CR	CR	CR
CR	PR	SD, PD or PR a
CR	SD	SD provided minimum criteria for SD duration met; otherwise, PD
CR	PD	SD provided minimum criteria for SD duration met; otherwise, PD
CR	NE	SD provided minimum criteria for SD duration met, otherwise NE
PR	CR	PR
PR	PR	PR
PR	SD	SD
PR	PD	SD provided minimum criteria for SD duration met, otherwise, PD
PR	NE	SD provided minimum criteria for SD duration met, otherwise NE
NE	NE	NE

CR = complete response, PR = partial response, SD = stable disease, PD = progressive disease, NE = nonevaluable.

a If a CR is truly met at first time point, then any disease seen at a subsequent time point, even disease meeting PR criteria relative to baseline, makes the disease PD at that point (since disease must have reappeared after CR). Best response would depend on whether minimum duration for SD was met. However, sometimes 'CR' may be claimed when subsequent scans suggest small lesions were likely still present and in fact the subject had PR, not CR at the first time point. Under these circumstances, the original CR should be changed to PR and the best response is PR.

Disease control is defined as BOR of CR, PR, or SD. Both CR and PR must be confirmed by repeat assessment performed at least 4 weeks after the criteria for response are first met. Confirmation of response must not necessarily be at the next scan, but could be at any subsequent scan before PD. When SD is believed to be the best response, the assessment must be at least 6 weeks after the start of a trial drug, and measurements must have met the SD criteria at least once. If the minimum time of 6 weeks is not met, the subject's BOR depends on the subsequent assessments. For example, a subject who has SD at the first assessment, PD at the second assessment and does not meet the minimum duration for SD, will have a BOR of PD. The same subject lost to follow-up after the first SD assessment would be considered NE for BOR.

DCR will be calculated by dose level and overall, along with the overall two-sided 95% CI using the Clopper-Pearson method (exact CI for a binomial proportion as computed by default by the FREQ procedure using the EXACT option).

The listing of tumor assessments (including e.g. lesion number, description and location, type of lesion, imaging date, assessment method, diameter (mm), sum of diameter of target lesions (mm), BOR (confirmed and unconfirmed) will be provided by subject as recorded from the "Target Lesions", "Sum of Diameters", "Non-Target Lesions", "New Lesions" and "Assessment of disease based on imaging" CRF pages.

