## 14.3 Swimlane Plots

A swimlane plot displaying some key radiological milestones will be produced, color-coded by planned dose level. Time in weeks will be displayed along the horizontal axis, and subject ID along the vertical axis. Subjects will be arranged from top to bottom in descending order of follow-up time. For each subject, the time from treatment start until end of follow-up will be represented by a horizontal bar. In addition, there will be different symbols to mark the following events: confirmed CR, confirmed PR, ongoing SD, PD, end of treatment, and death.

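### SAP Section 14.2 does not hold to one rule for objective response: it asks for confirmed CR/PR in some places and takes the best result at any scan just before the BOR/ORR table, which can raise ORR but never lower it

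*SAP*

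**What the plan says.** These statements in SAP Section 14.2 ask for confirmation:

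- The responder rate: "The BOR rate is defined as the number of subjects with BOR either confirmed CR or PR".
- DCR, which rests on each subject's "confirmed BOR according to RECIST 1.1 as assessed by the Investigator".
- Table 4, titled "Best Overall Response When Confirmation of Response is Required". Its row for CR followed by PD reads "SD provided minimum criteria for SD duration met; otherwise, PD", and the row for PR followed by PD applies the same rule. Neither row can end in a response.

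The swimlane plot in Section 14.3 likewise marks "confirmed CR, confirmed PR, ongoing SD, PD, end of treatment, and death".

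The text that leads into the BOR/ORR table does not ask for it. It states "BOR will be defined as the best response across all time points", illustrates this with a subject who has SD, then PR, then PD and is scored PR, tabulates BOR, and adds "The ORR will be defined as the rate of subjects who achieve either a CR or PR".

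The listing is to carry both versions: "BOR (confirmed and unconfirmed) will be provided by subject". No sentence says which version feeds the table.

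Protocol Section 7.3 counts only confirmed responses in its BOR rate and makes a scan at least 4 weeks later mandatory for any CR or PR. Protocol Appendix III gives the any-scan rule, with the same SD, PR, PD example, under the heading for studies that do not require confirmation. SAP Section 7, which lists departures from the protocol, does not mention a move to unconfirmed response.

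**The concern.** The example in the SAP is the case on which the two rules disagree. A subject with SD, PR, PD is a responder under the sentence before the table and a non-responder under Table 4. The SAP appears to have taken over the Appendix III paragraph meant for the other kind of study.

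Two programmers could therefore each follow Section 14.2 and produce different response tables. The responder rate near the start of the section and the ORR later in it could also differ, with nothing to tell the reader why. BOR is a named secondary endpoint in SAP Section 5.1, and Section 4 allows the results into the study report, regulatory submissions and manuscripts. In those places a summary ORR may be read without the by-subject listing.

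The plan leaves room for unconfirmed responses. Scheduled scans are 8 weeks apart and later 12 (SAP Section 14.1), subjects without progression at End of Treatment are not followed for progression (protocol Section 7.3), and the study ended early (SAP Section 6).

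**Working it through.** Neither document states a target, an assumed rate or a count for response, so there is no plan figure to reproduce.

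**Inputs**

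- Ordering CR, PR, SD, PD, NE; any-scan rule; ORR; 95% Clopper-Pearson interval: SAP Section 14.2.
- Confirmation at least 4 weeks later, at any later scan before PD; SD at least 6 weeks after start: SAP Section 14.2, text after Table 4.
- Planned size 24 to 30, with the scenario 4 × 3 + 2 × 6 = 24: protocol Section 8.1.
- Reporting by planned dose level: SAP Section 9.
- Scans within 7 days before Day 1 of Cycles 3, 5 and 7, then every 3 cycles: protocol Section 7.2.5. Cycle 3 Day 1 is study day 57, with a window from day 54: SAP Table 2.

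**1. The SAP's own example.** For SD, PR, PD the any-scan rule takes the highest category, PR, so the subject is a responder. Under the confirmed rule the PR has no second response before PD. With the 6-week minimum met, BOR is SD, so the subject is not a responder.

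**2. Direction.** A confirmed responder has at least two scans showing CR or PR before PD, and therefore at least one. Every confirmed responder is also an any-scan responder, so on the same assessments ORR(any scan) ≥ ORR(confirmed).

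**3. Check by enumeration.** Take all sequences of 1 to 4 scheduled scans over the five categories, stopped at the first PD. There are 5 + 20 + 80 + 320 = 425. The any-scan rule raises responder status in the sequences with exactly one CR or PR: 2 + 10 + 32 + 88 = 132. It lowers status in 0 and leaves 425 − 132 = 293 unchanged. These are counts of patterns, not probabilities. CR followed by PR was scored as a confirmed PR; scoring it as a non-response would only widen the gap.

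**4. Size, with assumed counts.** For x = 0 the upper limit is 1 − 0.025^(1/n); for n = 24 this is 1 − 0.025^(1/24) = 14.2%. For x = 1 the lower limit is 1 − 0.975^(1/n), and the upper limit is the 97.5% quantile of Beta(2, n − 1).

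| n | no responder (95% CI) | one unconfirmed PR counted (95% CI) |
|---|---|---|
| 3 | 0% (0 to 70.8) | 33.3% (0.8 to 90.6) |
| 6 | 0% (0 to 45.9) | 16.7% (0.4 to 64.1) |
| 24 | 0% (0 to 14.2) | 4.2% (0.1 to 21.1) |
| 30 | 0% (0 to 11.6) | 3.3% (0.1 to 17.2) |

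**5. DCR.** The earliest scheduled scan is day 54 − 7 = day 47, which is 46 days or 46/7 = 6.6 weeks after Day 1 and so beyond the 6-week minimum. An unconfirmed PR then becomes SD, which still counts as disease control. In the enumeration, disease control status differed in 0 of 425 sequences. Only an earlier, unscheduled scan could change it.

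**The case against.** The best defence is that Section 14.2 can be read in order: unconfirmed BOR and ORR go in the table, then a new paragraph brings in confirmed BOR for DCR. The listing shows that the authors had both versions in mind. Protocol Section 7.3 itself defines BOR as the best result over all visits up to progression, and it names objective response without defining an ORR. The protocol conflict is therefore confined to the numerator of the rate. The endpoint is descriptive, DOR and time to response have been dropped, and an ORR from a cohort of 3 says little under either rule.

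Much of this stands. Part of the ambiguity comes from the protocol, and the consequences are limited. But the sequential reading does not remove the conflict. It still reports responders whom the BOR rate in protocol Section 7.3, repeated in SAP Section 14.2, leaves out, and it would be a change from the protocol that SAP Section 7 does not declare.

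Two further points are fair. The claim about direction assumes that both rules use the same assessments, and Section 14.2 gives two end points for the window: documented progression, and end of treatment or progression. The denominators are also worded differently, since the BOR rate does not name the Safety Analysis Set that Section 14 uses for efficacy. Neither point changes the conclusion.

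**Conclusion.** The concern holds. As written, the text governing the BOR/ORR table applies a rule that the protocol reserves for studies without confirmation, and it contradicts the confirmed rate, Table 4 and the DCR basis in the same section. Given the same assessments, the effect on ORR is upward or nil, and it is nil if every response is confirmed.

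The sizes shown rest on assumed responder counts and on planned numbers that early termination may not have reached. One unconfirmed PR adds 1/24 = 4.2 percentage points overall and 1/3 = 33.3 points in a cohort of 3. No test depends on this endpoint, DCR is unaffected at scheduled scans, and a discrepancy could be traced by subject through the listing and the swimlane plot. It should be corrected, but it does not threaten the primary safety conclusions.

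**What to change.** In SAP Section 14.2:

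1. State that the tabulated BOR, the ORR and the DCR all use confirmed BOR: Table 4 together with the text after it (CR and PR confirmed at least 4 weeks later, at any later scan before PD; SD at least 6 weeks after start). Keeping that text matters, because the Table 4 row for PR followed by SD, read alone, could score PR, SD, PR as a non-response.
2. Define ORR as confirmed CR or confirmed PR, and say that it is the same quantity as the BOR rate, with the Safety Analysis Set as denominator.
3. Delete the any-scan sentence and its example, or relabel them as unconfirmed BOR. Keep the ordering CR, PR, SD, PD, NE, since Table 4 has no rows starting with SD or PD.
4. Use one assessment window throughout the section.
5. Show unconfirmed BOR in the listing. If an unconfirmed ORR is also wanted, label it as supplementary and note it in Section 7.

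The cost is wording only, with no new data. Compared with the any-scan rule on the same assessments, ORR can only stay the same or fall.
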